7. STATISTICAL ANALYSES

7.1 Case Selection

The enrollment period is expected to be 3-6 months. Around 200 primary care physicians and other physicians whose scope of practice includes disease screening, and/or diagnosis and management of patients with esophageal disease in the United States will be invited and a minimum of 100 will participate.

7.2 Power Justification

No data exist regarding the expected endoscopy referral rate for patients at risk for BE with an EsoGuard test result by primary care physicians. It is expected that if at least 100 providers participate and complete both rounds the objectives can be met. Previous randomized controlled, virtual patient trials enrolled between 81 and 202 participants (Peabody, 2019).

7.3 Statistical formulation and statistical analysis plan of the objectives

Primary objective: To determine the impact of EsoCheck/EsoGuard on health care provider's decision for upper endoscopy referral.

The impact will be measured by assessing the change in the percentage/rate of virtual patient cases who will be referred for endoscopy in the intervention round compared to the control round.

Statistics summarizing the agreement between the EsoGuard result (positive or negative) and the health care provider's decision (referral or no referral deemed necessary) include:

- positive agreement; percentage of EsoGuard positive virtual patient cases that were referred for endoscopy
- negative agreement; percentage of EsoGuard negative virtual patient cases that were not referred for endoscopy
- positive predictive value (PPV); percentage of referred virtual patient cases that are EsoGuard positive
- negative predictive value (NPV); percentage of non-referred virtual patient cases that are EsoGuard negative
- percentage of concordance

The participant-reported impact of EsoGuard results on their clinical decision making will be measured by assessing the proportion of patient cases in round 2 for which the provider answered the question, *“Did the EsoGuard result influence your decision to refer or not refer the patient for upper endoscopy”*, with, *“Yes; the EsoGuard result had an impact on my decision”* divided by all patient cases in round 2.

The provided answers will also be reported in a table with counts and percentages.

Secondary objective: To determine the impact of EsoCheck/EsoGuard on health care provider's patient risk assessment for BE.

The impact will be measured by assessing the change in the provider's virtual patient risk assessment for BE in the intervention round compared to the control round.

The provided answers will be reported in a table with counts and percentages.

The baseline and self-assessment questions, Round 1 Control, and Round 2 Intervention, will be reported in a table with counts and percentages.

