6. STUDY PROCEDURES

The participants will complete two rounds of questions concerning the assessed risk for BE and upper endoscopy referral of 6 patient cases (clinical vignettes). Per round, there will be 3 different questionnaires consisting of 6 clinical vignettes (A/B/C). Participants will be randomized to questionnaire A, B or C according to the randomization scheme.

The link to the online questionnaires will be sent by email. The questionnaires should be completed within approximately ten (10) business days, and no more than twenty (20) business days after receiving the link.

After the first round has been completed, an EsoCheck/EsoGuard information package and the second round of 6 clinical vignettes including EsoGuard results will be sent.

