6.1 Round 1 Control

The control round consists of 8 virtual patient cases (clinical vignettes). The 3 questionnaires (A/B/C) will consist of 6 clinical vignettes with the same risk profile as in the intervention round with a different description and in a different order.

The following baseline and self-assessment questions will be asked:

- Location of practice
- Type of practice
- Number of MDs associated with the practice
- Years of practice
- Proportion of patients covered by Medicare/Commercial insurance (<50% Medicare/>50% commercial; 50/50; >50% Medicare/<50% commercial)
- Estimate of number of GERD patients seen per week (<10; 10-20; ≥20)
- Rate your knowledge of Barrett's Esophagus (BE), esophageal adenocarcinoma (EAC), and associated risk factors (1 = not knowledgeable at all; 2 = not very knowledgeable; 3 = somewhat knowledgeable; 4 = very knowledgeable; 5 = expert)
- Rate your knowledge of the options and indications for BE screening (1 = not knowledgeable at all; 2 = not very knowledgeable; 3 = somewhat knowledgeable; 4 = very knowledgeable; 5 = expert)
- Rate the frequency in which you refer your GERD patients for endoscopic BE screening, as part of your standard practice (<20%; 20-40%; 40-60%; 60-80%; ≥80%)

The following questions will be asked per clinical vignette:

1. What level of risk for BE (and/or EC) do you think this patient has?
 - Low
 - Intermediate
 - High
2. Do you refer this patient for upper endoscopy?
 - Yes, I would refer this patient for endoscopy
 - No, I would not refer this patient for endoscopy

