6.2 Round 2 Intervention

The intervention round consists of 8 EsoGuard patient cases (clinical vignettes) (3 positive and 5 negative for EsoGuard). The 3 questionnaires (A/B/C) will have the same 5 negative EsoGuard cases, and 1 (different) positive EsoGuard case per questionnaire.

The following questions will be asked per clinical vignette:

1. What level of risk for BE (and/or EC) do you think this patient has?
 - Low
 - Intermediate
 - High
2. Do you refer this patient for upper endoscopy?
 - Yes, I would refer this patient for endoscopy
 - No, I would not refer this patient for endoscopy
3. Did the EsoGuard result influence your decision to refer or not refer the patient for upper endoscopy?
 - Yes; the EsoGuard result had an impact on my decision
 - No; the EsoGuard result had no impact on my decision

The following self-assessment questions will be asked of each participant at the end of round two (scale 1 very low to 5 high):

- Rate your understanding of EsoCheck/EsoGuard and its indications?
- How likely are you to use EsoCheck/EsoGuard for BE screening in your own practice?
- How likely are you to refer this technology to others or use in their practices?

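### The primary referral change pools 1 EsoGuard-positive and 5 EsoGuard-negative cases, so opposite effects partly offset, and no referral change by EsoGuard result is specified.

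*Combined protocol and SAP*

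**What the plan says.** Under the primary objective, section 7.3 lists three kinds of measure.

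- **Referral change.** The "change in the percentage/rate of virtual patient cases who will be referred for endoscopy in the intervention round compared to the control round". This is the only measure that compares referral between rounds, and it is stated for all cases together.
- **Agreement with the EsoGuard result.** For example, "positive agreement; percentage of EsoGuard positive virtual patient cases that were referred for endoscopy", with the matching figure for negatives, PPV, NPV and concordance. These need an EsoGuard result, which only the Round 2 vignettes carry.
- **Self-reported influence.** The count of yes answers "divided by all patient cases in round 2".

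Section 7.3 also promises tables of answers with counts and percentages, but it does not say whether they are laid out by vignette or by EsoGuard result. The secondary objective compares rounds on assessed risk, not on referral, and states no split by result.

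The case mix is fixed in section 6.2: the three questionnaires have the "same 5 negative EsoGuard cases, and 1 (different) positive EsoGuard case per questionnaire". Section 6.1 says that the Round 1 questionnaires hold "6 clinical vignettes with the same risk profile as in the intervention round with a different description and in a different order", so each Round 2 case should have a Round 1 counterpart. Section 7.2 states: "No data exist regarding the expected endoscopy referral rate for patients at risk for BE with an EsoGuard test result".

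**The concern.** The objective is the effect of the test on the referral decision. If physicians act on the result, referral should rise for the positive case and fall for the negative ones. The plan does not say this, but its agreement statistics imply it, since they count referral of positives and non-referral of negatives as agreement. Averaging the two movements into one net figure mixes effects of opposite sign, with weights set by the choice of vignettes.

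Net referral is a legitimate measure for a test presented as an alternative to endoscopy. Alone, it cannot show whether decisions moved in the expected direction after each result. At a low Round 1 rate, a pooled change near zero could mean that the test did nothing, or that referral of positives rose sharply while referral of negatives fell modestly. At a high Round 1 rate it mostly reflects the negatives. The study is meant to supply clinical utility data for reimbursement, and a split by result produced only after the data are seen would be post hoc.

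**Working it through.** **Inputs.** From the documents: 1 positive and 5 negative cases per questionnaire (section 6.2), and at least 100 participants (section 7.1). Referral rates and correlations are not given, so all of those below are assumptions. The plan has no figure of its own to reproduce here, because section 7.2 states no effect size, alpha or power.

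**Identity.** Let d_pos and d_neg be the Round 2 minus Round 1 referral changes for the positive and negative profiles. Then

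pooled change = (d_pos + 5 × d_neg)/6.

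The two parts cancel fully only when d_pos = -5 × d_neg.

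**1. Size of the offset.** Assume that 90% of positives and 10% of negatives are referred in Round 2, with the same Round 1 rate for both. The Round 2 overall rate is (90 + 5 × 10)/6 = 23.3%.

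| Round 1 rate | d_pos | d_neg | Pooled change |
|---|---|---|---|
| 20% | +70 | -10 | 23.3 - 20 = +3.3 |
| 30% | +60 | -20 | 23.3 - 30 = -6.7 |
| 50% | +40 | -40 | 23.3 - 50 = -26.7 |
| 70% | +20 | -60 | 23.3 - 70 = -46.7 |

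**2. Precision in the 20% row, N = 100.** Let r be the correlation between answers of one participant within a round and c the correlation across rounds. The answer variances are 0.2 × 0.8 = 0.16 in Round 1 and 0.9 × 0.1 = 0.09 in Round 2 (sum 0.25). The cross-round covariance is c × 0.4 × 0.3 = 0.12c. The 95% half-widths, as proportions, are:

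- pooled: 1.96 × sqrt((0.25 × (1 + 5r)/6 - 0.24c)/100)
- positives: 1.96 × sqrt((0.25 - 0.24c)/100)
- negatives: 1.96 × sqrt((0.25 × (1 + 4r)/5 - 0.24c)/100)

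| Setting | Pooled (+3.3) | Positives (+70) | Negatives (-10) |
|---|---|---|---|
| r = c = 0 | 4.0 | 9.8 | 4.4 |
| r = c = 0.15 | 3.8 | 9.1 | 4.1 |
| r = 0.4, c = 0 | 6.9 | 9.8 | 7.1 |

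For the positive case c cannot exceed 0.167, because the rate moves from 20% to 90%. In every row the pooled interval includes zero and both intervals by result exclude it.

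**3. Can the Round 2 statistics fill the gap?** Compare two scenarios with the same Round 2 rates, 95% of positives and 41% of negatives referred.

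- No effect: 95% and 41% in Round 1 as well. Overall rate (95 + 5 × 41)/6 = 50.0% in both rounds.
- Effects of +45 and -9: 50% and 50% in Round 1. Overall rate 50.0% in both rounds.

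In both, the pooled change is 0.0, positive agreement 95% and negative agreement 59%. Per participant, 0.95 + 5 × 0.41 = 3.00 cases are referred and 3.00 are not. So PPV = 0.95/3.00 = 31.7%, NPV = 5 × 0.59/3.00 = 2.95/3.00 = 98.3%, and concordance = (0.95 + 2.95)/6 = 65.0%. The pooled change and all five agreement statistics are identical. Self-reported influence, the risk-level change and the answer tables could still differ.

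**4. Limit of the problem.** With a common Round 1 rate b (in percent), d_pos is at most 100 - b, so full cancellation needs a fall in negatives of no more than (100 - b)/5: 16, 14, 10 or 6 points at b = 20, 30, 50 or 70. Larger falls cannot be fully hidden.

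**The case against.** The strongest reply is that much is already reported by result. Positive agreement, and 100% minus negative agreement, are the Round 2 referral rates by result. Only the matching Round 1 rates are missing, and a per-vignette table would show them. That is true, but the layout is not stated, and a table that might show the change is not a specified analysis of it.

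The offset is also inferred. No document gives a direction or a Round 1 rate, and at 50% or 70% in the first table nothing is hidden. This stands as a limit. It is not a defence, because the plan itself has no data with which to rule out a low rate.

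Some illustrations are fragile. The pooled interval in the 20% row includes zero at N = 100, but 100 is a minimum: by the same formula it excludes zero from 145 participants at r = c = 0 and from 128 at r = c = 0.15. The widest half-widths need strong consistency within a round and none across rounds, which is unlikely. For negatives, r = c = 0.4 would give 3.6, below the tabulated range. The two-scenario comparison is a constructed tie, with unequal Round 1 rates in one scenario. It shows that the statistics cannot separate effect from no effect in general, not that such a tie is likely.

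Finally, an educational package is sent between rounds and the vignette descriptions differ, so a change by result still mixes education and wording with the test result. This limits attribution. It does not remove the gain from seeing the direction of change.

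**Conclusion.** The concern holds and should be fixed. That the measure is pooled, that negatives carry 5/6 of the weight, and that no Round 1 to Round 2 referral change by EsoGuard result is specified all follow from sections 6.2 and 7.3 without assumption. The size of the offset does rest on assumed rates. It is large when Round 1 referral is low and small when it is high. The pooled measure is not wrong in itself, but alone it does not answer whether each result moved decisions as expected.

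**What to change.** In section 7.3, keep the pooled change and label it as specific to the 1:5 case mix. Beside it, under the primary objective, pre-specify the referral change from Round 1 to Round 2 for (a) the EsoGuard-positive profile and (b) the five EsoGuard-negative profiles. Compare each within participant with the Round 1 vignette of the same risk profile, and give 95% intervals that allow for several answers per participant. Tabulate the risk-level change and the self-reported influence by EsoGuard result.

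In section 6, which now says "Participants will be randomized to questionnaire A, B or C according to the randomization scheme", confirm that each participant receives the corresponding questionnaire in both rounds.

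The cost is a few sentences in 7.3 and one in section 6. No new data are needed, because the referral question is asked for each vignette in both rounds. The downside is two more results to report, and (a) rests on one case per participant. At N = 100 under assumed rates:

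- For (a), 50% to 90%, the half-width is 1.96 × sqrt((0.34 - 0.30c)/100): 11.4 points at c = 0, 10.4 at c = 0.2 and 9.6 at the maximum c of 0.333.
- For (b), 50% to 30%, it is 1.96 × sqrt((0.46 × (1 + 4r)/5 - 2c × 0.2291)/100): from 4.6 points (r = c = 0.4) to 9.6 (r = 0.4, c = 0), with 5.9 at r = c = 0.

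### The primary change in endoscopy referral is planned as a pooled percentage with no measure of precision and no change by EsoGuard result, although the same physicians answer risk-matched vignettes in both rounds.

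*Combined protocol and SAP*

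**What the plan says.** Section 7.3 measures the primary impact as the "change in the percentage/rate of virtual patient cases who will be referred for endoscopy in the intervention round compared to the control round". The unit counted is the case, and no summary per physician is defined. The section then lists positive and negative agreement, PPV, NPV and concordance between the EsoGuard result and the referral decision, and the share of round 2 cases in which the physician reports that the result mattered. The only reporting format named is of this kind: "The provided answers will also be reported in a table with counts and percentages". Similar sentences cover the risk assessment and the two rounds.

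Section 7.2 gives no alpha, power, effect size or target precision. It says: "It is expected that if at least 100 providers participate and complete both rounds the objectives can be met".

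Three other places set the structure of the data:

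- Section 6: "The participants will complete two rounds of questions concerning the assessed risk for BE and upper endoscopy referral of 6 patient cases".
- Section 6.1: the round 1 questionnaires hold "6 clinical vignettes with the same risk profile as in the intervention round", described differently and in a different order.
- Section 6.2: "The 3 questionnaires (A/B/C) will have the same 5 negative EsoGuard cases, and 1 (different) positive EsoGuard case per questionnaire".

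**The concern.** Each physician contributes six answers to round 1 and six to round 2, on vignettes of matching risk. Two features of such data determine the precision of the change. A physician's answers tend to resemble each other within a round, which widens the interval. A physician's answers also tend to resemble each other across rounds, which narrows it. Round totals show neither. A reader given only counts and percentages cannot tell a precisely estimated change from one compatible with very little effect. An analyst who adds an interval later would choose the unit of analysis after seeing the data.

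The second problem is the case mix. If physicians follow the test, referral should fall in the five negative cases and may rise in the one positive case. The pooled change adds these with weights 5/6 and 1/6, so opposite movements partly cancel. The agreement statistics compare decisions with the test result. They do not show how far each group moved from round 1, which is what the primary objective asks.

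**Working it through.** The plan states no precision, so there is no figure of its own to reproduce. The documents give 100 physicians (7.2), six vignettes per round (6) and the 5-to-1 mix (6.2). Referral totals, response patterns and correlations are assumptions, since 7.2 says no data on referral rates exist.

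**1. Same totals, different precision.** Assume 360/600 referred in round 1 and 300/600 in round 2, a change of -10 points.

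Treating all answers as independent:

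SE = sqrt(0.6×0.4/600 + 0.5×0.5/600) = 2.86 points

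-10 ± 1.96×2.86 gives -15.6 to -4.4.

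For the paired analysis, let d be a physician's change in number of referrals divided by 6, with n = 100, SE = SD(d)/10 and the t distribution on 99 degrees of freedom. In each pattern below the changes sum to -60 referrals and only follow the test: negatives only lose referrals and the positive only gains one.

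| Pattern (change in referrals per physician) | SE | Paired 95% interval |
|---|---|---|
| (a) 60 at -1, 40 at 0 | 0.82 | -11.6 to -8.4 |
| (b) 30 at -3, 30 at +1, 40 at 0 | 2.72 | -15.4 to -4.6 |
| (c) 26 at -5, one at -3, 73 at +1 | 4.42 | -18.8 to -1.2 |

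Pattern (c) is close to the largest spread possible under these rules. Pattern (b) happens to lie near the independent-answers interval.

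**2. What the pooled -10 stands for.** Pooled change = 5/6 × change in negatives + 1/6 × change in the positive.

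| Pattern | Negatives (paired 95% interval) | Positive |
|---|---|---|
| (a) | -60/500 = -12.0 (-14.0 to -10.0) | 0 |
| (b) | -90/500 = -18.0 (-23.5 to -12.5) | +30/100 = +30 |
| (c) | -133/500 = -26.6 (-35.4 to -17.8) | +73/100 = +73 |

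Check: 5/6×(-12.0) + 0 = -10; 5/6×(-18.0) + 30/6 = -10; 5/6×(-26.6) + 73/6 = -10.

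**3. General size.** With six vignettes per round, equal variances, within-round correlation ICC and cross-round correlation c, the ratio of the true SE to the independent-answers SE is sqrt(1 + 5×ICC - 6×c).

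| ICC | c = ICC | c = 0.8×ICC | c = 0.5×ICC | c = 0 |
|---|---|---|---|---|
| 0.1 | 0.95 | 1.01 | 1.10 | 1.22 |
| 0.2 | 0.89 | 1.02 | 1.18 | 1.41 |
| 0.3 | 0.84 | 1.03 | 1.26 | 1.58 |

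At 50% referral in both rounds the independent-answers half-width is 1.96×sqrt(2×0.25/600) = 5.7 points. At ICC 0.3 the four columns give 4.7, 5.8, 7.2 and 8.9 points.

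**4. Coverage by simulation.** Each setting used 4,000 runs of 100 physicians with six exchangeable vignettes per round. Physician effects were on the logit scale, and average referral was about 64 to 66% in round 1 and 42 to 44% in round 2.

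- Where physicians differed only in overall tendency to refer (SD 1 or 1.5), the nominal 95% independent-answers interval covered 96 to 97%.
- Where the round effect also varied between physicians (SD 1, 1.5 and 2, with tendency SD 1), it covered 92%, 88% and 85%.
- The interval from the 100 paired differences covered 94 to 95% in all of these settings.

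**The case against.** The strongest reply is that nothing in the plan is shown to be wrong. It states no hypothesis test and prespecifies no incorrect interval. With six answers per round, the pooled change among completers equals the mean within-physician change, so the headline number would stay the same. Physician-level answers are collected, and an interval can be added at any time. If physicians are consistent across rounds, an interval that ignores the structure has about the right width. All this is true, and it makes the defect an omission rather than an error. It does not supply the precision, or settle the method before the data are seen.

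A second reply is that round 2 is already split by result: positive agreement is the referral rate in positives, and one minus negative agreement is the rate in negatives. This also stands, but it is half of a change. If the planned table of the two rounds is laid out by vignette, the other half could be read from it; the text does not say that it will be.

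Third, the magnitudes are constructed. Pattern (c) is extreme, and all three intervals exclude zero. The column with no cross-round correlation fits poorly with matched vignettes answered by the same people. If the ICC is defined within vignette, the pooled variance also contains between-vignette differences fixed by design, and the ratios overstate the problem. These points limit how far the sizes can be taken as predictions. They leave the main fact: round totals do not determine precision.

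Finally, the sentence on counts and percentages follows the question on reported influence and may refer only to that item. The conclusion does not depend on it, because no other section plans an interval either.

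**Conclusion.** The concern holds. Followed as written, the plan gives a headline change in referral with no measure of its precision and no change from round 1 by EsoGuard result. Clustering does not bias the estimate among completers. Under the assumed totals, one and the same -10 points has a paired SE anywhere from 0.82 to 4.42. For assumed ICCs of 0.1 to 0.3, the true SE is 0.84 to 1.58 times the independent-answers SE, and close to it when the cross-round correlation is about 0.8 of the ICC. Neither the direction nor the size of the discrepancy can be known before the data, which is the reason to specify a method that is right in either case. This should be changed, but it does not invalidate the design.

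**What to change.** In section 7.3, define the primary estimate as the mean within-physician change in referral percentage, round 2 minus round 1, among physicians who complete both rounds. Give a 95% interval from the t distribution or a bootstrap that resamples physicians. State how many complete round 1 only.

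Report the same estimate and interval for the five EsoGuard-negative vignettes. For the positive vignette, report the change against the round 1 vignette of the same risk profile, with an interval for a paired difference in proportions. This requires that a physician keeps the same questionnaire letter in both rounds, which the protocol does not state and should. If the letter is not kept, the difference in referral rates with a physician-bootstrap interval would serve instead.

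Any intervals for negative agreement, PPV, NPV, concordance and reported influence should be clustered by physician. Positive agreement rests on one answer per physician and does not need this.

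The cost is SAP wording, a few lines of code and a little more analysis work. No new data are needed. Some intervals will be wider than a calculation that treats every answer as independent.

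### The self-reported influence measure pools five negative cases with one positive case per physician, so it cannot show which result drove it or whether referral differed from Round 1

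*Combined protocol and SAP*

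**What the plan says.** Under the primary objective, section 7.3 lists several measures. The first is the "change in the percentage/rate of virtual patient cases who will be referred for endoscopy in the intervention round compared to the control round". Next come agreement statistics between the EsoGuard result and the Round 2 referral decision, among them positive and negative agreement. The last is participant-reported impact: the number of cases answered "Yes; the EsoGuard result had an impact on my decision", "divided by all patient cases in round 2". The answers are also to be tabulated with counts and percentages, with no stratification stated.

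Section 6.2 asks, for each vignette, "Did the EsoGuard result influence your decision to refer or not refer the patient for upper endoscopy". The only alternative to Yes is "No; the EsoGuard result had no impact on my decision". The same section fixes the case mix: the three questionnaires have the "same 5 negative EsoGuard cases, and 1 (different) positive EsoGuard case per questionnaire".

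Section 6.1 says that the Round 1 vignettes match the Round 2 vignettes on risk profile but differ in description and order. Section 3 places an educational package between the rounds. Section 7.2 expects the objectives to be met if "at least 100 providers participate and complete both rounds", and says that no data exist on expected referral rates with an EsoGuard result.

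**The concern.** Two kinds of information are lost in this one percentage.

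The first is the test result. A positive and a negative result push the referral decision in opposite directions, and the agreement statistics in the same section keep them apart. The influence measure does not. Its value is a weighted average whose weights come from the questionnaire design, not from any patient population.

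The second is the referral decision itself. The question asks about influence, with no category that separates a changed decision from a confirmed one. A physician who would not have referred anyway, and was reassured by a negative result, may truthfully answer Yes. So may one whose decision reversed. The plan collects a Round 1 answer for a profile-matched case from the same physician but does not link it to this item.

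The synopsis and section 2 say that the trial is meant to supply clinical utility data for reimbursement. A percentage labelled impact will be read in that light, and a reader could not tell from it whether positive results, negative results, changed decisions or reassurance lay behind it.

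**Working it through.** The plan gives no expected value, target or test for this measure, so there is no figure to reproduce. The inputs from the documents are five negative cases and one positive case per physician (section 6.2), a denominator of all Round 2 cases (section 7.3), and at least 100 completers (section 7.2). All Yes rates and referral rates below are assumptions.

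**1. Weights.** With 100 completers there are 100 × 6 = 600 cases, of which 500 are negative and 100 positive. The negative share of the denominator is 5/6 = 83.3%.

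**2. Pooled figure.** Let y_neg and y_pos be the Yes proportions on negative and positive cases. Then pooled = (5 × y_neg + y_pos)/6.

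- Moving y_pos from 0 to 100% changes the pooled figure by 1/6 = 16.7 points.
- Yes on all positives and no negatives: 1/6 = 16.7%.
- Yes on all negatives and no positives: 5/6 = 83.3%.
- y_neg 60%, y_pos 95%: (3.00 + 0.95)/6 = 65.8%.
- y_neg 74%, y_pos 25%: (3.70 + 0.25)/6 = 65.8%.

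Solving 5 × y_neg + y_pos = 3.95 shows how little that value says about positives. It fits any y_pos from 0 (with y_neg = 3.95/5 = 79%) to 100% (with y_neg = 2.95/5 = 59%).

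**3. Yes answers and changed decisions.** Let r_neg and r_pos be the Round 1 referral rates for the profiles that are EsoGuard-negative and EsoGuard-positive in Round 2. Suppose every physician follows the result in Round 2 and answers Yes every time, so that reported influence is 100%. The share of decisions that changed is (5 × r_neg + (1 − r_pos))/6.

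| r_neg | r_pos | Changed | Excess of reported influence |
|---|---|---|---|
| 0% | 100% | 0% | 100 points |
| 20% | 80% | 20.0% | 80 points |
| 50% | 50% | 50.0% | 50 points |
| 90% | 50% | 83.3% | 16.7 points |
| 100% | 20% | 96.7% | 3.3 points |

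The first and last rows are the extremes of the grid examined (r_neg 0 to 100%, r_pos 20 to 100%). The gap is large when few negative-profile cases are referred in Round 1, and small when nearly all are.

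**4. Whether the other measures fill the gap.** The change in referral rate is a net figure in which opposite switches cancel. At r_neg 10% and r_pos 50% with full adherence, changed decisions are (0.5 + 0.5)/6 = 16.7%. The Round 1 referral rate is (5 × 0.10 + 0.50)/6 = 16.7% and the Round 2 rate is 1/6 = 16.7%, so the net change is zero. Positive and negative agreement are split by result but use neither the influence question nor Round 1.

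**The case against.** The strongest reply is that the plan calls this item participant-reported and never equates it with changed decisions. It stands beside a between-round referral comparison and result-specific agreement statistics, and it has no target, test or stated prominence. That is fair: it is a supporting descriptive measure, and the point leaves the referral comparison untouched.

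The planned table might also be laid out by vignette. Each Round 2 vignette has a fixed EsoGuard result, so the split by result would then be visible. The text neither states nor excludes this layout, and it would still not supply the link to Round 1.

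Three stronger readings are tempting, and the documents do not support them.

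- A reader might infer that the plan counts confirmation as impact. The wording permits this but does not require it; a physician whose decision was confirmed may answer Yes or No.
- A reader might infer that 83% of the Yes answers come from negatives. That share describes the denominator. In the two 65.8% examples, negatives supply 3.00/3.95 = 76% and 3.70/3.95 = 94% of the Yes answers; if only positives drew a Yes, they would supply none.
- A reader might infer that the reported figure will far exceed the share of changed decisions. Any single gap rests on assumed rates, and the range above is too wide to establish that.

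It can also be objected that a differing answer between rounds is not proof of a changed mind. This stands. The match is by risk profile and not by identical vignette, and education comes between the rounds. Calling the cells impact and confirmation would therefore be unsound.

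**Conclusion.** The point holds as a matter of interpretability. Sections 6.2 and 7.3 alone establish that the pooled percentage carries a design-fixed weight of 83.3% on negatives, cannot show which result drove it, and is not linked to whether the referral answer differed from Round 1. The other planned outputs do not supply that link.

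The possible excess over changed decisions is real in principle but of unknown size: 3.3 to 100 points over the assumed grid, under full adherence and universal Yes answers. With fewer Yes answers it would be smaller. The documents therefore do not support a claim that the measure will overstate impact by a given amount, or that the primary objective as a whole fails. This is a cheap improvement to one descriptive measure.

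**What to change.** In section 7.3:

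1. Report the Yes proportion separately for EsoGuard-positive and EsoGuard-negative cases. Describe any pooled figure as perceived influence, and state the five-to-one case mix beside it.
2. As a descriptive supplement, cross-tabulate Yes/No against whether the same physician's referral answer differed between the risk-profile-matched Round 1 and Round 2 vignettes, within each EsoGuard result.
3. State the matching key, including whether a physician keeps the same questionnaire letter in both rounds. The documents do not say so explicitly, and matching the positive case depends on it.
4. Label the cells as differed or did not differ between matched profiles. Note that the different descriptions and the educational package mean a difference cannot be attributed to the EsoGuard result alone.

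The question, the sample and the procedures stay as they are. The cost is one extra table from data already collected, and possibly a less favourable figure. The positive stratum will also be less precise: with 100 completers it has one case per physician, so at an assumed 50% Yes the 95% half-width is 1.96 × √(0.5 × 0.5/100) = 9.8 points.
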